Therapy Modes for Helix Ventilator

The device that is being evaluated in this study can provide many different modes of therapy in both pressure support and volume controlled ventilation.

The following is a list of modes that may be provided with these devices, dependent on patient prescriptions:

- Continuous Positive Airway Pressure (CPAP) with optional C-Flex
- Spontaneous Pressure Support (S) with optional Bi-Flex
- Spontaneous/Timed Pressure Support (S/T)
- Pressure Control Pressure Support (PC)
- Timed Pressure Support (T)
- Averaged Volume Assured Pressure Support (AVAPS) in conjunction with the modes listed above (S, S/T, PC, T)
- Volume Control Ventilation (CV)
- Volume Assist Control (AC)
- Synchronous Intermittent Mandatory Ventilation (SIMV)
- Pressure Control SIMV (PC SIMV)
- Pressure Regulated Volume Control (PRVC)

Target Patient Population

The patient population is extremely varied. The patient's age will vary from infant ($\geq 5\text{kg}$) to adult. The medical condition of the patient population ranges from critically ill acute respiratory conditions to pre-existing or developing chronic conditions. Patients treated with the Helix ventilator may suffer from diseases or injuries requiring invasive or non-invasive ventilation. Many of these diseases result in respiratory failure, which can be classified as acute or chronic. Acute respiratory failure is typically treated in a hospital ICU or sub-acute hospital, while chronic respiratory failure is treated at home or in a long term care facility. Specific examples of respiratory failure include, but are not limited to:

- Neuromuscular diseases leading to respiratory failure: Amyotrophic Lateral Sclerosis (ALS), Spinal Muscular Atrophy (SMA), Duchenne Muscular Dystrophy (DMD)

Engineering Evaluation of the Helix Family of Ventilators

Confidential

HRC-17067-HCPED-CC Version: 2.0, 26-Oct-2018

Page 13 of 21

- Chronic Obstructive Pulmonary Disease (COPD)
- Asthma
- Spinal cord injuries
- Thoracic cage deformities
- Pneumonia originating from infectious disease such as influenza
- Pulmonary edema (symptom of congestive heart failure)
- Trauma leading to Acute Lung Injury (ALI)
- Acute Respiratory Distress Syndrome (ARDS)

II. Study Objective

The objective of this Engineering study is to verify the overall performance and controls of the Helix Ventilator.

Specific Aims

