This clinical study is a non-randomized, single site, single-arm engineering clinical comparison study. The study is designed to collect and compare device parameters from the patient's current ventilator compared to the Helix ventilator.

V. Participant Enrollment

Following initial contact by their physician or his/her surrogate, participants/surrogate will be informed that their participation is entirely voluntary and the decision to participate or not, will in no way affect their further evaluation or therapy. Subsequently, the participant or surrogate will be given a complete and thorough explanation of the benefits and risks or discomforts that may be anticipated with this study. Informed consent will be obtained prior to enrollment in the study.

Sample Size:

Up to thirty (30) participants will be recruited for this study.

Engineering Evaluation of the Helix Family of Ventilators

Confidential

HRC-17067-HCPED-CC Version: 2.0, 26-Oct-2018

Page 15 of 21

VI. Study Procedures

Following the completion of the informed consent, participants enrolled in this study will be asked to use their existing ventilator for up to 1 hour to collect pressure and flow data for comparison purposes against the Helix ventilator.

Participants will then be set up on the Helix Ventilatory System using the same mode of therapy as their current ventilator. Participants may receive mechanical ventilation using any patient circuit currently being designed for the Helix Ventilator (Passive, Active with PAP, Active with Flow, or dual limb). Patients currently using non-invasive ventilation may be asked to use a mouth piece in lieu of a mask interface. While using the study device, therapy setting may be altered by the physician or his/her surrogate while maintaining the ventilator needs of the patient. For e.g., a patient currently prescribed an SIMV mode may temporarily be switched to a pressure control mode to assess patient synchrony and ventilator performance.

Once the participant is set-up, he/she will be asked to use the ventilator for up to 4 hours. During this time, Philips Respiration engineers will be collecting data through several mechanisms: 1) Helix SD Card, 2) NICO Monitoring System, and / or 3) External data collection device (ex. laptop). The study staff may ask the participant's opinions on the comfort of the therapy delivery. There will be no invasive monitoring as part of this study.

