The engineering evaluations will take place at the Boston Children's Health Physician offices. The study investigators, respiratory therapist, and/or other qualified clinical staff, will be supervising and present for all study visits. Philips Respiration engineers will be present for observational purposes only. All study staff working on this trial will be trained to the protocol and device prior to beginning work.

Participants may be asked to participate in this data collection study up to six (6) times.

Study data collected for this study will be collected on paper or electronic source records. These records will include information regarding inclusion/exclusion, performed study procedures and questions regarding device use. Only those staff that have been delegated by the Principal Investigator will be able to enter or make changes to the data in the Case Report Forms.

Engineering Evaluation of the Helix Family of Ventilators

Confidential

HRC-17067-HCPED-CC Version: 2.0, 26-Oct-2018

Page 16 of 21

VII. Statistical Analysis

The purpose of this Engineering study is to collect engineering and subjective data on the Helix Ventilatory System and the patient's existing ventilator device for comparison purposes. Therefore, no formal analysis of the data is planned.

Determination of Sample Size

Up to 30 participants will be enrolled in the study. Since this is an engineering study to address issues which arise, no sample-size calculation was performed.

General Considerations

The primary analysis will be performed including all completed participants. Descriptive data tables will be provided for all variables of interest. Continuous data will be presented by mean, standard deviation, median, minimum, and maximum observation. Data will be presented in the untransformed and transformed format (if applicable) for each continuous variable. Categorical data will be presented as frequencies and percentages. All analyses will be conducted using either SAS® or SPSS® software.

Participant Disposition

Participant disposition, including the total number of participant's enrolled, completed, early terminations and withdrawals, will be presented overall and by software version. A listing will be provided with the reasons for discontinuation.

Demographics and Baseline Characteristics

Standard subject demographics (e.g., age and gender) and baseline characteristics will be summarized for all participants enrolled and for evaluable participants.

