Trends Analysis

The aim of this Engineering study is to verify the performance and controls of the Helix Ventilator. If formal significance testing is required, the endpoints will be compared between the device versions, including device hardware, software,

For continuous data, within-subject comparisons between two iterations will be performed using paired t-tests or the non-parametric Wilcoxon Signed-Ranks test, depending on the distribution of the data.

Within-subject comparisons across three or more iterations will be done using Repeated-Measures Analysis of Variance (RMANOVA) or the non-parametric Friedman Test. For participants who only try one iteration throughout the trial, between-subjects comparisons across two iterations will be done using independent-samples t-tests or the Mann Whitney test. If between-subjects comparisons are made across

Engineering Evaluation of the Helix Family of Ventilators

Confidential

HRC-17067-HCPED-CC Version: 2.0, 26-Oct-2018

Page 17 of 21

three or more iterations, ANOVA or the Kruskal-Wallis test will be employed. Post-hoc pairwise comparisons will include an appropriate alpha adjustment.

If formal analysis of categorical data is required, methods such as the Fisher's Exact or Chi Squared Test will be used for between-subjects comparisons, and the McNemar Test or Cochran's Q will be used for within-subject comparisons.

All tests will be conducted at a significance level of $p < 0.05$.

Treatment Compliance

It is expected that the drop-out rate will be low as the study is an engineering trial.

Safety Analysis

Safety evaluations will be performed by recording clinical adverse events at the time originally reported, and they will be followed at each visit thereafter until resolution. Adverse events will be provided in data listings.

Interim Analysis

There is no interim analysis planned for this study.

VIII. Risks and Discomforts

The risks of providing ventilatory support with the study device are no greater than the risks encountered with other ventilatory support devices.

The devices that will be used by the subject have been tested to ensure safety. Should the device not perform as designed, ventilation could increase and decrease more than desired. This effect could be uncomfortable. Should any problems be identified, the respiratory therapist will remove the study device and resume ventilatory support with the participant's current device.

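### For participants who try only one iteration, the version tests leave the own-ventilator data unused, which costs nearly all power on endpoints that scale with body size

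*Combined protocol and SAP*

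**What the plan says.** Section VII opens by stating that "no formal analysis of the data is planned", and its sample-size paragraph adds that "no sample-size calculation was performed". Trends Analysis then sets out tests for use if needed: "If formal significance testing is required, the endpoints will be compared between the device versions". Participants who try two versions get a paired t-test or Wilcoxon signed-rank test, and those who try three or more get repeated-measures ANOVA or Friedman. Only for those who try a single iteration does it say that "between-subjects comparisons across two iterations will be done using independent-samples t-tests or the Mann Whitney test", with ANOVA or Kruskal-Wallis for three or more versions. No covariate, stratum or baseline term is named. "All tests will be conducted at a significance level of" 0.05.

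Three other places bear on this branch:
- Section I, Target Patient Population: "The patient population is extremely varied", from infants of at least 5 kg to adults. Section III sets the same lower limit and no upper one.
- Section VI: "participants enrolled in this study will be asked to use their existing ventilator for up to 1 hour to collect pressure and flow data". This comes before Helix set-up, and its stated purpose is comparison with Helix.
- Section V: "Up to thirty (30) participants will be recruited for this study". Section IV describes the study as non-randomised and single-arm.

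The own-ventilator data enter no test in Trends Analysis.

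**The concern.** In the between-subjects branch, different people on different versions are compared. Tidal volume and peak flow, both listed in Aim 6, depend on body size. Across a range from 5 kg to adult, the spread between people in such quantities is likely to be far larger than any plausible difference between versions. An unadjusted test then has little chance of detecting a real version change.

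The study already collects a pre-Helix reading that carries most of that between-person spread, and this branch does not use it.

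There is also a risk of bias. Versions are not allocated at random, and no rule balances body size across them. If, for instance, later versions were tried mainly on smaller children, the size difference would appear as a version difference.

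**Working it through.** **Plan's own figure.** The only figure is up to 30 participants, with no effect size, SD or power behind it, so there is nothing to reproduce. The calculations below are illustrations.

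**Inputs from the document.** Significance level 0.05 (sidedness not stated, two-sided assumed), at most 30 participants, weight from 5 kg upwards.

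**Assumed inputs.** An even split of 15 versus 15, which is a best case; a true 10% version shift; a weight-proportional quantity with a 15% coefficient of variation (CV) per kg; weight ranges from 5-20 kg to 5-80 kg.

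**Step 1: spread of the unadjusted reading.** CV = √[(1 + CV_weight²)(1 + 0.15²) − 1].
- Weight uniform on 5-20 kg: CV_weight = (15/√12)/12.5 = 0.346, so CV = √(1.120 × 1.0225 − 1) = 0.381.
- Weight log-uniform on 5-80 kg: mean = 75/ln 16 = 27.05, mean square = 6375/(2 ln 16) = 1149.6, CV_weight = 0.756. So CV = √(1.571 × 1.0225 − 1) = 0.779.

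The other ranges tried lie between these two.

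**Step 2: power of the unadjusted test.** Power ≈ Φ[0.10/(CV × √(2/15)) − 1.96], with √(2/15) = 0.365.
- CV 0.381: Φ(0.719 − 1.96) = 0.107.
- CV 0.779: Φ(0.352 − 1.96) = 0.054.

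The smallest shift detectable with 80% power is 2.80 × 0.365 × CV, or 39% and 80% of the mean. For 80% power at a 10% shift, the number per version is 2(1.96 + 0.842)² × CV²/0.10². With unrounded CVs this is 228 to 953, against at most 30 in total.

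Simulation (3,000 runs, 5-80 kg log-uniform) gives 4.6% power for the t-test and 4.2% for Mann-Whitney. With no version effect the rejection rates are 5.1% and 4.4%, so chance imbalance does not inflate the error rate.

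A log transformation alone does not help. With weights log-uniform on 5-70 kg, the t-test on logs has about 6% power.

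**Step 3: using the own-ventilator value.** Let each device's reading scatter by s (log scale) around the participant's true level. The log ratio of Helix to own ventilator then has SD s√2, and the shift is ln 1.1 = 0.0953. Power ≈ Φ[0.0953/(s√2 × 0.365) − 1.96]. The simulations use 3,000 runs per setting and weights log-uniform on 5-70 kg.

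| s per device | Formula | ANCOVA, simulated | Mann-Whitney on log ratio, simulated |
|---|---|---|---|
| 5% | 96% | 95% | 94% |
| 10% | 45% | 43% | 41% |
| 20% | 15% | 14% | 13% |

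In the same simulations the unadjusted t-test had 6-7% power and Mann-Whitney 5-6%. ANCOVA's type I error was about 5%. With weights 10-40 kg and s = 10%, the comparison is 9% for the unadjusted t-test against 42% for ANCOVA.

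**Step 4: when Helix settings differ.** Add 20% scatter to the Helix reading at s = 10%. The SD of the log ratio is √(0.10² + 0.10² + 0.20²) = 0.245, so power ≈ Φ(0.0953/(0.245 × 0.365) − 1.96) ≈ 19% by the formula. Simulated ANCOVA gives about 17%.

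**Step 5: size of a possible bias.** If mean weight differs systematically by 20% between version groups, a weight-proportional quantity differs by about 20% with no device effect. That is twice the 10% shift assumed above.

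**The case against.** The strongest reply is that the plan never says the endpoints are unadjusted Helix readings. The design exists to compare Helix with the participant's own ventilator, so a Helix-versus-own difference is at least as natural a reading. Applied to a relative difference with SD 10% (about 7% scatter per device, since 0.10/√2 = 0.071), the planned t-test already has power Φ(0.10/(0.10 × 0.365) − 1.96) = 78%. This stands: the gap is as much one of endpoint definition as of test choice. It does not remove the point, because nothing in Trends Analysis directs a difference, ratio or adjustment.

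A reader might infer more than the documents support:
- *That all between-version tests are affected.* They are not. Participants who try two or more versions get paired or repeated-measures tests, which remove stable body size, and Section VI allows up to six participations.
- *That body size swamps every version effect.* Percent error against a set or control value, synchrony, comfort and usability need not scale with weight.
- *That chance differences in who met which version create false positives.* The 5% level already covers these. Only systematic imbalance would bias the test.

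There are also fair limits on the gain. Section VI allows settings, mode, circuit and interface to change on Helix, so the own-ventilator hour is not always like for like. It names only pressure and flow, so tidal volume would have to be derived from flow. The plan does not say that the hour is repeated at later visits. At 20% scatter per device, even ANCOVA reaches only 14% power.

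**Conclusion.** The point holds for one contingent branch: between-subjects comparisons of size-dependent endpoints among participants who try a single iteration. If those endpoints are analysed as Helix readings, power for a 10% version shift is roughly 5-11% at 15 versus 15, and systematic size differences between non-randomised groups could bias the result. Using the own-ventilator value gives about 95%, 43% or 14% power at 5%, 10% or 20% scatter per device, and less if settings or circuit differ on Helix.

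The weight distributions, scatter, effect size and even split are all assumptions, because the documents give none of them. The low power of the unadjusted test holds under every weight range tried; the size of the gain depends on how closely the two devices' readings agree within a person. Severity is minor: formal testing is conditional, and no conclusion stated in the plan depends on this branch.

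**What to change.** In Trends Analysis, define each endpoint. For between-subjects comparisons of quantities also available from the own-ventilator hour:
- Replace the independent-samples t-test or ANOVA by ANCOVA: regress the Helix value (log scale for volume and flow) on version, with the own-ventilator value as covariate.
- Apply Mann-Whitney or Kruskal-Wallis to the Helix-minus-own difference, or to the log ratio for volume and flow.
- Preferably use Helix recording segments in the same mode, circuit and interface as the own device. This is a choice of data for analysis and does not change how participants are set up.

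Leave the within-subject tests, and endpoints that do not scale with size, as they are.

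The cost is a few sentences and one degree of freedom in the model. No new data are needed. Participants without an own-ventilator reading are excluded from that model, and their number should be reported.
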